9.3.3.2 Demographics and other characteristics

1. Demographics: date of birth, gender, race, BMI, occupation, and family history
 - Family history includes asthma, COPD, bronchiectasis, and lung cancer
2. Smoking status: former, current smoker, or non-smoker
3. COPD-related history and comorbidities
 - COPD-related history:

The data to be documented include date of diagnosis (ICD-9-496 or ICD-10-J44.9), disease severity on index date of starting LABA/LAMA or LAMA therapy (GOLD grade: GOLD 1, 2, 3, 4; GOLD group: A, B, C, or D), results of COPD assessments (CAT and mMRC, see the definitions in the **Section 9.3.3.4** and **9.3.3.5**), spirometry results (FEV₁ and FVC, see **Section 9.3.3.6**), and acute exacerbations (see **Section 9.3.3.3**).

According to the COPD guideline (version 2017),⁶ patients will be graded and grouped by disease severity based on the results of COPD assessments and spirometry. Detailed criteria are presented in **Figure 1**.

[figure not shown]

Figure 1 Disease severity of COPD

- Comorbidities of interest:

Comorbidities regarding any medical findings from 6 months before the index date* until death or 1 year after the index date should be collected as below.

- Cardiovascular disease: ischemic heart disease, heart failure, coronary artery disease, myocardial infarction
- Cerebrovascular disease: stroke
- Respiratory disease: pulmonary hypertension
- Hepatic disease: hepatitis
- Renal disease: chronic kidney disease, kidney failure
- Gastrointestinal disease: gastroesophageal reflux disease (GERD), GI bleeding, gastric disease
- Metabolic disease: diabetes mellitus [T1 or T2], hypertension, obesity, hyperlipidemia
- Infectious disease: pneumonia, respiratory tract infection, influenza, tuberculosis, viral infection
- Osteoporosis
- Anxiety
- Depression

*Index date: It is defined as the date of COPD patients in the cohort A and B starting using LABA/LAMA therapy regardless of new initiation or switching from other single/dual/triple treatment, or the date of the patients in the cohort C starting using LAMA treatment.

4. Hospitalization records:

These records from 1 year before the index date until death or 1 year after the index date should be collected.

Proprietary confidential information © 2019 Boehringer Ingelheim International GmbH or one or more of its affiliated companies

The hospitalization caused by COPD exacerbation (ICD-9: 491.21; ICD-10: J44.1) should be documented on the CRF, including admission/discharge date, treatments (doses, frequency, and the route of administration), and reasons for switching medications. Other hospitalizations unrelated to COPD exacerbation will not be recorded.

5. Laboratory data: eosinophils

The data nearest to the index date will be collected as the **Baseline** and will continue recording until death or 1 year after the index date.

Blood eosinophil counts are used for a standard of applying ICS treatment for patients with $\geq 2\%$ eosinophil counts.⁶ Additionally, higher blood eosinophils may incur greater exacerbations in patients treated with LABA only (without ICS).^{19,20} Eosinophils counts and assessment date will be recorded.

9.3.3.3 Acute exacerbation of COPD

The data from 1 year before the index date until death or 1 year after the index date should be collected.

Acute exacerbation is defined as a complex of lower respiratory events/symptoms (worsening or new onset) related to the underlying COPD, with a duration of 3 days or more, requiring a prescription of antibiotics and/or systemic steroids and/or hospitalization (should all be accompanied by code of ICD-9-491.21 or ICD-10-J44.1). Within the retrospective period, the onset/stop date of COPD exacerbation, severity* (mild, moderate, severe), and its outcome (leading to hospitalization/acute respiratory failure [ICD-9-518.81 or ICD-10-J96.00/J96.01/J96.02] or not) will be recorded. In terms of the exacerbation-related therapies, they will be recorded onto the page of “Rescue treatments” in the CRF.

***Mild exacerbation** is a patient with worsening but self-managed symptoms.

Moderate exacerbation is a patient receiving an exacerbation-related prescription such as oral corticosteroid (prednisone or prednisolone) and/or antibiotic, but not requiring hospitalization.

Severe exacerbation is a patient requiring hospitalization or emergency room visit due to COPD (ICD-9-491.21 or ICD-10-J44.1).

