1. Date of birth, gender, race, BMI, occupation, and family history
2. Date of diagnosis and disease severity (GOLD grade: GOLD 1, 2, 3, 4; GOLD group: A, B, C. or D)
3. Former, current smoker, or non-smoker
4. Cardiovascular (e.g., ischemic heart disease, heart failure, coronary artery disease, myocardial infarction), cerebrovascular (e.g., stroke), respiratory (e.g., pulmonary hypertension), hepatic (e.g., hepatitis), renal (e.g., chronic kidney disease, kidney failure), gastrointestinal (e.g., GERD, GI bleeding, gastric disease), metabolic (e.g., diabetes mellitus [T1 or T2], hypertension, obesity, hyperlipidemia), infectious (e.g., pneumonia, respiratory tract infection, influenza, tuberculosis, viral infection), osteoporosis, anxiety, and depression.
5. Score between 0 – 40 points
6. Score between 0 – 4 points
7. FEV₁ and FVC, etc.
8. The definition of an acute exacerbation is that a complex of lower respiratory events/symptoms (worsening or new onset) related to the underlying COPD, with a duration of 3 days or more, requiring a prescription of antibiotics and/or systemic steroids and/or hospitalization (ICD-9: 491.21; ICD-10: J44.1). Onset/stop date, severity (mild, moderate, severe), and leading to hospitalization/acute respiratory failure (ICD-9-518.81 or ICD-10-J96.00/J96.01/ J96.02) or not will be recorded.
9. **Hospitalizations caused by COPD exacerbation (ICD-9: 491.21; ICD-10: J44.1)** will be collected only. The information includes admission/discharge date, treatments for COPD, and reasons for switching medications.
10. Including SABA (fenoterol, salbutamol, terbutaline), SAMA (ipratropium bromide), LABA (indacaterol, olodaterol), LAMA (aclidinium bromide, glycopyrronium, tiotropium, umeclidinium), LABA + LAMA (FDC; tiotropium/olodaterol, indacaterol/glycopyrronium, vilanterol/umeclidinium), LABA + ICS (formoterol/beclothesone, formoterol/budesonide, salmeterol/fluticasone, vilanterol/fluticasone), triple therapies (free combo or vilanterol/umeclidinium/fluticasone [FDC]), or others (theophylline, roflumilast, mucolytics, etc.). Prescription date, doses, frequency, and reasons for switching medications will be recorded.

| Variables | Time points | Eligibility assessment | Data collection retrospectively | | |
|-----------|---|------------------------|---------------------------------|-------------------------|--------------------------------------|
| | | | Before the index date | Index date [#] | 1-year follow-up period [†] |

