| 11. | If a patient receiving SABA, SAMA, LABA/ICS or a triple therapy before LABA/LAMA treatment on the index date, the relevant information on the medications, doses, frequency, the route of administration, the reasons for switching medications should be recorded. | | | | |
| 12. | Prescription date, doses, and frequency will be recorded. | | | | |
| 13. | Therapies for the emergency/hospitalization regarding COPD (ICD-9: 491.21; ICD-10: J44.1) will be collected, including but not limited to short-acting bronchodilators, antibiotics, oral corticosteroid (e.g., prednisone or prednisolone), ventilator support, or oxygen therapy. Prescription date, doses, frequency, and the route of administration will be recorded. | | | | |
| 14. | NIPPV or IPPV for those not for rescue use | | | | |
| 15. | Including but not limited to surgeries for COPD or improvement of lung function. | | | | |

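### A self-managed mild exacerbation does not meet the protocol's own exacerbation definition, so the planned mild rate is essentially empty or off-definition; the moderate and severe wording also needs aligning with that definition

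*Combined protocol and SAP*

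**What the plan says.** Section 9.3.3.3 requires a lower respiratory episode lasting at least three days and "requiring a prescription of antibiotics and/or systemic steroids and/or hospitalization (should all be accompanied by code of ICD-9-491.21 or ICD-10-J44.1". Table 1, note 8, in section 9.2.3 gives the same condition and attaches the three grades to it: "requiring a prescription of antibiotics and/or systemic steroids and/or hospitalization (ICD-9: 491.21; ICD-10: J44.1). Onset/stop date, severity (mild, moderate, severe".

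The grades in section 9.3.3.3 are:

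- Mild: "is a patient with worsening but self-managed symptoms".
- Moderate: "is a patient receiving an exacerbation-related prescription such as oral corticosteroid (prednisone or prednisolone) and/or antibiotic, but not requiring hospitalization".
- Severe: "is a patient requiring hospitalization or emergency room visit due to COPD", with the same ICD codes.

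The abstract and section 9.3.2.2 list annualized rates for all three grades as a secondary outcome. Section 9.7.1 computes the rates by severity in each cohort and compares the three cohorts by rate ratios. The primary outcome (section 9.3.2.1) pools the moderate and severe grades as time to first event.

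**The concern.** The definition and the grades are meant to describe one set of episodes, but they do not cover the same set. The mild grade describes an episode with none of the treatments that the definition demands. The severe grade admits an ER visit, and the moderate grade gives its prescriptions only as examples; the definition contains neither an ER visit nor any prescription beyond antibiotics and systemic steroids. A non-admitted ER visit with a prescription also fits both the moderate and the severe wording.

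At stake is whether the mild rate measures anything, and whether the separate moderate and severe rates are reproducible across around 12 hospitals. No visible section settles these points. One entry between 9.7.1 and 9.7.3 is redacted in the table of contents, and the case report form (CRF) is not among the documents, so either might bear on them.

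**Working it through.** The plan gives no figure by grade to reproduce. The size section uses 0.78 and 0.90 events per patient-year without stating a grade, and the point does not depend on them. The check is a comparison of the rules as written.

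**Step 1: the rules.** Take the duration and ICD conditions as met. Describe an episode by four yes/no features: A, an antibiotic or systemic steroid; O, another exacerbation-related prescription; E, an ER visit; H, an admission. From section 9.3.3.3:

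- Definition met = A or H
- Mild = none of A, O, E, H
- Moderate = (A or O) and not H
- Severe = H or E

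**Step 2: all combinations.** There are 2 × 2 × 2 × 2 = 16. The definition fails only when A and H are both absent, which leaves 2 × 2 = 4 combinations, so 16 − 4 = 12 meet it. None of the 12 is mild. The four that fail are:

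| Care received | Definition met | Grade by wording |
|---|---|---|
| None of the four | No | Mild |
| ER visit only | No | Severe |
| Other prescription only | No | Moderate |
| Other prescription and ER visit | No | Moderate and severe |

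Three combinations are both moderate and severe (E present, H absent, with A, with O, or with both). The two that include A meet the definition.

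**Step 3: two consistent ways to apply the text.**

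- *Definition first.* Only episodes that meet the definition are graded. Mild is then 0 in each cohort and each mild ratio is 0/0. ER-only and other-prescription-only episodes are also left out, so they never reach the primary outcome.
- *Grades first.* Any episode that fits a grade is counted. Mild is then a count of charted self-managed worsening, outside the definition. ER-only episodes count as severe and other-prescription-only episodes as moderate, and either could be a first event in the primary analysis.

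The mild rate is unsatisfactory on both. The primary outcome is touched only on the second.

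**Step 4: how much of the plan is involved.** Three grades × 3 cohorts = 9 rates. Three cohorts give 3 pairwise contrasts, so 3 × 3 = 9 ratios, or 3 × 2 = 6 with one reference cohort. Mild supplies 3 of the 9 rates and 3 of the 9 ratios (2 of 6). This is 1 of the 5 outcomes in section 9.3.2.2.

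**Step 5: the moderate/severe overlap.** Moving an episode between these grades leaves their sum unchanged, so the pooled moderate-or-severe outcome is unaffected. The separate rates can move. The documents give no shares, so the following is an assumption: a share h of events is admitted, and a share f is a non-admitted ER visit with an antibiotic or steroid. The severe rate is rate × h if those visits are graded moderate and rate × (h + f) if graded severe. With h = 20% and f = 5% to 20%:

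- at 0.78: 0.78 × 0.20 = 0.156, against 0.78 × 0.25 = 0.195 to 0.78 × 0.40 = 0.312;
- at 0.90: 0.90 × 0.20 = 0.180, against 0.90 × 0.25 = 0.225 to 0.90 × 0.40 = 0.360.

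At 0.78, h = 10% gives 0.078 against 0.117 to 0.234, and h = 30% gives 0.234 against 0.273 to 0.390. With equal shares in both groups the ratio does not move: 0.156/0.180 = 0.312/0.360 = 0.867. The ratio changes only if the shares differ between cohorts, and nothing in the documents speaks to that.

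**The case against.** The natural order of section 9.3.3.3 is to define the event and then grade it. On that reading an ER visit or other prescription outside the definition is never graded, and it would be inconsistent to use the definition to empty the mild grade and then ignore it to say that excluded events reach the primary outcome. This stands: reach to the primary outcome holds only if the grades are applied without the definition.

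The severe grade names the ER visit outright and the moderate grade does not, so most abstractors on an ordered scale would take the higher grade. This largely stands. The missing precedence rule is a detail worth writing down, and the size of the overlap is unknown and may be nil.

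A patient who self-treats with antibiotics or steroids supplied earlier might be both self-managed and within the definition. The documents do not describe this case, and it would also fit the moderate wording. It is why the mild rate is called essentially empty rather than necessarily zero.

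Table 1, note 13, says "Therapies for the emergency/hospitalization regarding COPD (ICD-9: 491.21; ICD-10: J44.1) will be collected, including but not limited to short-acting bronchodilators, antibiotics, oral corticosteroid", and continues to ventilator support and oxygen. This shows that therapies outside the definition are recorded, not that any ER visit was treated with them alone.

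Physician training (section 9.8) and the data validation plan (section 9.6) might produce a common practice, but neither is said to address grading. The descriptive purpose of the study lowers the stakes but does not give the mild rate a meaning.

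**Conclusion.** The mild grade and the definition contradict each other as written, and the planned mild rate and ratios are uninterpretable however this is applied: essentially empty and not estimable, or off-definition and dependent on charting. That covers 3 of 9 rates and 3 of 9 pairwise ratios in one secondary outcome. It rests on reading self-managed as involving no prescription, ER visit or admission, and on the redacted entry and the CRF not resolving it.

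The ER-visit and prescription mismatch is real on the text but secondary. A reader might infer that the primary outcome is compromised. The documents do not support that: the moderate/severe overlap cancels in the pooled outcome, and any effect of ER-only or other-prescription-only episodes depends on grading without the definition and on subgroups whose size is not given. A reader might also infer from the timing sentence in section 9.7.1, which refers to the first exacerbation on the CRF without a grade, that mild episodes count as primary events. The sentence before it already restricts the outcome to moderate or severe.

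The wording should be corrected before lock. No bias in any rate ratio has been shown.

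**What to change.** Before database lock, reconcile the abstract, Table 1 note 8, and sections 9.3.2.2 and 9.3.3.3, and carry the result into the rate analysis in 9.7.1:

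1. Remove the mild rate and its rate ratio from the comparative secondary outcome, or report charted self-managed worsening descriptively, outside the exacerbation count.
2. Make the definition and the moderate and severe grades agree on which ER visits and prescriptions qualify. The direction is the sponsor's choice.
3. Assign each episode to exactly one grade by a written rule.
4. Report moderate, severe and moderate-or-severe rates.

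The cost is mostly wording and the loss of one uninformative measure. Admitted episodes can already be identified: for each exacerbation, "its outcome (leading to hospitalization/acute respiratory failure [ICD-9-518.81 or ICD-10-J96.00/J96.01/J96.02] or not) will be recorded", and admissions for exacerbation "should be documented on the CRF, including admission/discharge date" (section 9.3.3.2). ER visits without admission may need site queries. If the sponsor widens the definition, episodes left off the exacerbation record may require some charts to be re-reviewed, which costs more than a query. Section 6 plans data collection to end on 30 November 2019, five days after this version's date of 25 November 2019, so queries need to be raised promptly.

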9.3.3.4 COPD assessment test (CAT)

The data nearest to the index date will be collected as the **Baseline** and will continue recording until death or 1 year after the index date.

The COPD assessment test (CAT) is a simple, 8-item, health status instrument which provides a simple method for assessing the impact of COPD on the patient's health and the quality of life. The total CAT score ranging from 0 - 40 is calculated by summing the points for each variable. A decrease in CAT score represents an improvement in health status, whereas an increase in CAT score represents a worsening in health status.²¹ The most reliable estimate of the minimum significant difference in the CAT score is 2 points.²²

9.3.3.5 modified Medical Research Council dyspnea scale (mMRC)

The data nearest to the index date will be collected as the **Baseline** and will continue recording until death or 1 year after the index date.

mMRC is a 4-item questionnaire for measuring the severity of dyspnea of patients, and the score is correlated with health status²³ and mortality^{24,25} for patients with respiratory disease. If mMRC scale of the patient is > 2, it means the patient may suffer from dyspnea.

9.3.3.6 Spirometry results

The data nearest to the index date will be collected as the **Baseline** and will continue recording until death or 1 year after the index date.

Spirometry is the most common tool to evaluate the lung function of patients with respiratory disease. Among the results of spirometry, FEV₁ and the ratio of FEV₁/FVC are well-known for assisting in the diagnosis, determining disease severity, and following up the prognosis.^{6,26,27} In general, patients may be suspected to have COPD based on the criteria including post-bronchodilator FEV₁ < 80% predicted and FEV₁/FVC ratio < 70% in accordance with GOLD guideline (version 2017).⁶

9.3.3.7 Treatments

Treatments for COPD will be recorded in the CRF within the retrospective duration, including medications related to COPD, rescue treatments, and oxygen therapies, etc.; of which, prescription date, doses, frequency, the route of administration, and reasons for switching medications will be recorded. Above information (except for rescue treatments) will be recorded every 6 months from 6 months before the index date until death or 1 year after the index date, whichever occurs first.

In addition, pharmacological therapies for comorbidities will also be documented and information will be recorded every 6 months from 6 months before the index date until death or 1 year after the index date, whichever occurs first.

- Related to COPD:

Medications of interest

- SABA: fenoterol, salbutamol, and terbutaline
- SAMA: ipratropium bromide
- LABA: indacaterol and olodaterol
- LAMA: aclidinium bromide, glycopyrronium, and tiotropium, umeclidinium
- LABA + LAMA: tiotropium/olodaterol, indacaterol/glycopyrronium, and vilanterol/umeclidinium (FDC)
- LABA + ICS: formoterol/bclomethasone, formoterol/budesonide, salmeterol/fluticasone, and vilanterol/fluticasone

Proprietary confidential information © 2019 Boehringer Ingelheim International GmbH or one or more of its affiliated companies

- Triple therapies: free combo or vilanterol/umeclidinium/fluticasone (FDC)
- Others: theophylline, roflumilast, and mucolytics, etc.

Rescue treatments

Therapies for the emergency or hospitalization regarding COPD will be collected, including but not limited to the following list:

- Short-acting bronchodilators: SABA (fenoterol, salbutamol, or terbutaline) or SAMA (ipratropium bromide)
- Antibiotics, only record those for respiratory infections
- Oral corticosteroid: prednisone or prednisolone
- Ventilator support: noninvasive (nasal/facial mask) or invasive (orotracheal tube or tracheostomy), or oxygen therapies

Others

Non-pharmacological therapies, including but not limited to the following:

- Oxygen therapy: collecting the therapy for maintenance such as noninvasive positive pressure ventilators (NIPPV) or intermittent positive pressure ventilation (IPPV)
- Surgery, especially relating to COPD or improving the lung function
- Related to comorbidities

Pharmacological therapies for comorbidities of interest (see **Section 9.3.3.2**) will be collected.

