| Study design: | 
This is a retrospective, multi-center, cohort study to collect the data on COPD patients who were administered with LABA/LAMA (FDC or free combo) or LAMA treatment for 3 months at least prior to 30 June 2018. For LABA/LAMA therapy, new initiation or switching from other therapy (i.e., single/dual/triple) are both acceptable; for LAMA
 | | |

Proprietary confidential information © 2019 Boehringer Ingelheim International GmbH or one or more of its affiliated companies

| | |
|--------------------|---|
| | 
treatment, only new initiation will be acceptable. The data abstracted from eligible patients will be recorded only when they are available in the medical chart and will be categorized into the cohort A (patients treated with Tio + Olo), B (patients treated with other LABA/LAMA therapy), and C (LAMA therapy).
 
The follow-up period for each patient will be from the index date* until the date of death or 1 year after the index date, whichever occurs first. Patients will be censored at the time from one LAMA/LABA or LAMA switched to another LAMA/LABA or ICS.
 
*Index date: It is defined as the date of COPD patients in the cohort A and B starting using LABA/LAMA therapy regardless of new initiation or switching from other single/dual/triple treatment, or the date of the patients in the cohort C starting using LAMA treatment.
 |
| Population: | 
This study plans to review the medical chart from approximately 1,800 COPD patients receiving LABA/LAMA or LAMA treatment for 3 months at least prior to June 30 2018 in Taiwan.
 
Inclusion criteria
 
Patients who fulfil ALL the following criteria are included.
 
1. Patients who diagnosed with COPD who were prescribed with LABA/LAMA (FDC or free combo) as a new initiation or switching from other therapy (i.e., single/dual/triple), or newly receiving LAMA treatment for 3 months at least prior to 30 June 20182. Male or female patients ≥ 40 years of age 
Exclusion criteria
 
Patients who meet the following criterion are not included.
 
1. Patients with documented diagnosis of bronchial asthma, asthma-COPD overlap syndrome (ACOS), bronchiectasis, cystic fibrosis, or lung cancer |

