| Variables: | 
Variables
 
• Patient demographics (date of birth, gender, race, body mass index [BMI], family history, occupation, etc.)• Diagnosis of COPD (date of diagnosis, disease severity, etc.)• Smoking status• Spirometry data (e.g., FEV₁, FVC)• COPD assessments (e.g., CAT, mMRC)• Acute exacerbations from 1 year before the index date until 1 year after the index date or the date of death (onset/stop date, etc.)• Hospitalizations due to COPD exacerbation (e.g., admission/discharge date, treatments)• Laboratory data (e.g., eosinophil counts) |

Proprietary confidential information © 2019 Boehringer Ingelheim International GmbH or one or more of its affiliated companies

| | |
|-----------------------|--|
| | 
• Pharmacological/non-pharmacological treatments from 6 months before the index date to 1 year after the index date or the date of death, especially for the following:
- Treatment related to COPD (start/stop dates, dosage, frequency, etc.)- Rescue treatments for COPD (antibiotics, oral corticosteroid, ventilator support, etc.)- Oxygen therapies- Surgeries for COPD therapy or improvement of lung function• Time/reasons for treatment switching (e.g., single/dual/triple therapy to LABA/LAMA prior to the index date, Tio + Olo to other therapies, single/dual escalating to dual/triple therapy)• Comorbidities (cardiovascular, cerebrovascular, respiratory, hepatic, renal, gastrointestinal, metabolic, infectious comorbidities, etc.) |
| | 
Primary outcomes
 
• Time to the first moderate or severe COPD exacerbation |
| | 
Secondary outcomes
 
• Annualized rate of mild/moderate/severe exacerbation• Time/reason (e.g., severe airflow limitation, diagnosis of asthma, worsening exacerbation) from LABA/LAMA escalating to LABA/LAMA/ICS or from LAMA to dual therapy• Percentage of patients receiving LABA/LAMA switched to triple therapy or LAMA switched to dual therapy• Change in pulmonary function after LABA/LAMA or LAMA initiation• Use of rescue medications |
| Data sources: | Source data are collected from medical charts in 12 medical hospitals in Taiwan. The case report form (CRF) will be designed for the data collection. |
| Study size: | Approximately 1,800 eligible COPD patients are planned to be enrolled from 12 medical hospitals in Taiwan. |

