9.2.3 Study visits

The abstracted data will be recorded on the case report form (CRF). **Table 1** shows the collected data at different retrospective period of the medical chart.

Table 1 Data collection schedule

| Variables | Time points | Eligibility assessment | Data collection retrospectively | | |
|----------------------------------|-------------|------------------------|---------------------------------|-------------------------|--------------------------------------|
| | | | Before the index date | Index date [#] | 1-year follow-up period [†] |
| Eligibility assessments | X | | | | |
| Demographics ¹ | | | | X* | |
| Diagnosis of COPD ² | | | | X* | |
| Smoking status ³ | | | | X* | |
| Comorbidity ^{4, §} | | X [◊] | X | X | |
| COPD assessments [‡] | | | | | |
| CAT ⁵ | | X ^Δ | X | X | |
| mMRC ⁶ | | X ^Δ | X | X | |
| Examinations [‡] | | | | | |
| Spirometry data ⁷ | | X ^Δ | X | X | |
| Eosinophils | | X ^Δ | X | X | |
| Records [‡] | | | | | |
| Acute exacerbations ⁸ | | X ^{&} | X | X | |
| Hospital admissions ⁹ | | X ^{&} | X | X | |
| Treatments | | | | | |

| Variables | Time points | Eligibility assessment | Data collection retrospectively | | |
|--|-------------|------------------------|---------------------------------|-------------------------|--------------------------------------|
| | | | Before the index date | Index date [#] | 1-year follow-up period [†] |
| Related to COPD ^{10, \$} | | | X ^{11, ♦} | X | X |
| Related to comorbidities ^{12, \$} | | | X [◊] | X | X |
| Rescue treatments ^{13, ‡} | | | X [◊] | X | X |
| Oxygen therapy ^{14, \$} | | | X [◊] | X | X |
| Others ^{15, \$} | | | X [◊] | X | X |

[#]Not later than 30 June 2018; defined as the date of COPD patients in the cohort A and B starting using LABA/LAMA therapy regardless of new initiation or switching from other single/dual/triple treatment, or the date of the patients in the cohort C starting using LAMA treatment

[†]Not later than 1 year after the index date

^{*}The data nearest to the index date will be collected.

[◊]The data 6 months before the index date will be documented.

^{\$}The data will be collected every 6 months (allowed window: ± 1 month).

[‡]All available data on the medical chart will be recorded.

[△]The data nearest to the index date will be collected as the **Baseline**.

[&]The data/events ever since patients started receiving LABA/LAMA or LAMA therapy will be collected (maximum: trace back to 1 year before the index date).

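### The six-monthly recording rule for COPD maintenance treatment conflicts with the start, stop and switch dates promised in the abstract and needed for censoring and time to escalation

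*Combined protocol and SAP*

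**What the plan says.** Two recording rules apply in Table 1 (section 9.2.3). Exacerbations, admissions, rescue treatments, CAT, mMRC and spirometry carry the double-dagger footnote: "All available data on the medical chart will be recorded". The row for COPD treatment, which holds the regimens that define the three cohorts, carries the dollar-sign footnote instead: "The data will be collected every 6 months (allowed window: ± 1 month".

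Section 9.3.3.7 agrees with the table. It lists the items to be abstracted ("prescription date, doses, frequency, the route of administration, and reasons for switching medications will be recorded") and then sets the interval: "Above information (except for rescue treatments) will be recorded every 6 months from 6 months before the index date", running to death or one year after index. Note 10 to Table 1 has a similar item list: "Prescription date, doses, frequency, and reasons for switching medications will be recorded". Neither list contains a stop date.

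The abstract promises more. Its variables include "Treatment related to COPD (start/stop dates, dosage, frequency, etc" and, as a separate item, "Time/reasons for treatment switching (e.g., single/dual/triple therapy to LABA/LAMA prior to the index date", with moves from Tio + Olo to other therapies and escalation among its examples.

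The analyses depend on these dates. The abstract says: "Patients will be censored at the time from one LAMA/LABA or LAMA switched to another LAMA/LABA or ICS". For the primary outcome, section 9.7.1 names censoring only at escalation to ICS. It also analyses time to escalation to dual or triple therapy by Kaplan-Meier curves and log-rank tests. Sections 9.7 and 9.7.3 rule out imputation.

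**The concern.** The date on which a patient leaves the index regimen ends time at risk for the primary outcome and is itself the event for a secondary outcome. The plan has an all-records rule but does not apply it to the treatment that fixes this date. In at most one year of follow-up, a six-monthly schedule gives about two records after index, near months 6 and 12.

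If a site enters only the regimen current at those points, with the prescription then in force, three things can happen. An exacerbation after a switch is credited to the regimen the patient has left. A change made and reversed between two points never appears. The time-to-escalation curve gathers its steps near months 6 and 12. Section 9.3.2.2 names worsening exacerbation among the example reasons for escalating, so the misplaced months could be months of above-average risk. With no imputation, analysts could not recover dates that were never abstracted. With about 12 sites, different readings of the rule would also make the error depend on site.

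**Working it through.** The plan gives no figure for this point, so there is none to reproduce. The check first sets the texts side by side and then sizes the worst case.

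**What the schedule can mean.** Table 1 places the index date no later than 30 June 2018, and follow-up lasts at most one year, so all follow-up ends by 30 June 2019. Section 6 plans data collection from 1 August to 30 November 2019; the abstract says July to November 2019. On either timetable follow-up is over before abstraction starts, and abstraction lasts less than six months. The six-month interval with its window therefore cannot be a calendar for abstraction work. It reads most naturally as time points within the chart. A second reading is possible: abstraction by six-month period, with every dated prescription entered. The text does not choose between them.

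**Inputs for the worst case.** Records fall at months 6 and 12 (Table 1; the ± 1 month window is ignored at first). At least 3 months of therapy is required (sections 9.1 and 9.2.2), so switches are taken as uniform over months 3 to 12. The share s of patients who switch is not in the documents and is assumed at 10%, 20% or 40%. Event rates are 0.78 and 0.90 per patient-year (section 9.5). The recorded date is assumed to be the one at the recording point, not the first prescription.

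**Mean delay.** One third of switches fall in months 3–6 (mean delay 1.5 months) and two thirds in months 6–12 (mean delay 3 months): 1/3 × 1.5 + 2/3 × 3 = 2.5 months = 0.2083 year. The maximum is 6 months, or about 7 with the window (one record at month 5, the next at month 12).

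**Misattributed time.** The mean switch time is 7.5 months, so a switcher loses 4.5/12 = 0.375 year of on-regimen time. Misattributed time per patient is s × 0.2083, and true on-regimen time is 1 − 0.375s. Expected misattributed events per 1,000 patients are 1,000 × s × 0.2083 × rate.

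| Assumed s | Misattributed / on-regimen (years) | Share | Events per 1,000 (0.78 to 0.90) |
|---|---|---|---|
| 10% | 0.0208 / 0.9625 | 2.2% | 16 to 19 |
| 20% | 0.0417 / 0.925 | 4.5% | 33 to 38 |
| 40% | 0.0833 / 0.85 | 9.8% | 65 to 75 |

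**First event credited to the old regimen.** For a patient event-free at the switch, with a constant rate r, average 1 − exp(−r × delay) over the delay. For delays uniform on 0–3 months this is 9.1% (r = 0.78) or 10.5% (r = 0.90); for 0–6 months it is 17.2% or 19.5%. Weighted 1/3 and 2/3, the result is 14.5% or 16.5%.

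**Temporary changes.** A change lasting L months escapes both records with probability (3 − L)/3 (zero if L ≥ 3) when it starts in months 3–6, and (6 − L)/6 when it starts in months 6–12. Weighted 1/3 and 2/3:
- L = 1: 1/3 × 2/3 + 2/3 × 5/6 = 78%
- L = 2: 1/3 × 1/3 + 2/3 × 4/6 = 56%
- L = 3: 2/3 × 3/6 = 33%
- L = 4: 2/3 × 2/6 = 22%

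**Other reading.** If the first prescription date of each new regimen is abstracted, the delay for a lasting switch is 0 and the table above becomes zero. Under snapshots, a change reversed between points is still missed.

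**The case against.** The strongest reply is that the dates are listed data items. The prescription date and switch reasons stand in the sentence just before the six-month rule and in note 10, and the abstract adds start and stop dates and the time of switching. For a lasting switch, the first prescription date of the new regimen is the switch date, so a stop date is not needed to censor or to time escalation. The dollar-sign footnote also governs the row for other treatments, which note 15 says includes surgeries. A surgery is a point event and cannot be sampled as current status, which favours abstraction by period.

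Much of this stands. A reader might infer that switch dates will be late or missed; the documents support only that they may be, under the snapshot reading. For lasting switches, the date must in addition not be the first prescription. A reader might also picture a patient moved to triple therapy at month 2. On the ordinary reading of the three-month requirement that patient may not qualify, and a mean delay of 3 months, which assumes switches over the whole year, is too long. Nor is a differential error between Tio + Olo and other LABA/LAMA shown: section 9.3.2.2 names the same step up for both.

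What does not fall away is that the interval applies, by its own words, to the list that contains the prescription date. Nothing says how a switch between two points is dated, and the body and the abstract list different dates.

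**Conclusion.** The concern holds as an inconsistency with a real risk to the data, not as a demonstrated loss of dates. Followed literally, a stated recording rule can misdate or miss the events that drive censoring and escalation, so this is more than a missing detail. The 2.5-month mean delay and the 2.2% to 9.8% of on-regimen time are worst-case figures. They rest on snapshot sampling, a non-first prescription date, evenly spread switches and assumed switch shares.

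Which switches matter for the primary outcome is itself unsettled. The abstract censors at a move to another LAMA/LABA or to ICS, whereas section 9.7.1 names only escalation to ICS. Either rule needs an exact date. The CRF is not among the documents and may already hold the dates. This should be fixed, with moderate confidence.

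**What to change.** Reconcile the abstract's variable list, Table 1 with its footnotes, note 10 and section 9.3.3.7:

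- In Table 1, move COPD maintenance medicines from the dollar-sign footnote to the double-dagger all-records footnote. In section 9.3.3.7, extend the exception for rescue treatments to these medicines.
- In note 10 and section 9.3.3.7, require the first-prescription (start) date and the stop date of every maintenance COPD regimen, from 6 months before index to the end of follow-up.
- In section 9.7.1, state that censoring and time to escalation use those dates. Align its censoring rule with the abstract so that it is clear which switches count.

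The cost is wording changes to the protocol and CRF and somewhat more abstraction time per chart; the all-records rule already applies to exacerbations and rescue treatments. If the CRF already holds the dates, only a clarification is needed. This protocol version is dated 25 November 2019 and data collection was planned to end on 30 November 2019. Any charts already abstracted as snapshots would therefore have to be reopened.
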